### 4.2 EFFICACY ASSESSMENTS

The same blinded evaluator should perform EGW/PAW counting at Screening, Baseline and Weeks 2, 4, 8, and 12. In the event that this is not possible due to unforeseen circumstances, a different blinded evaluator will evaluate the subject. However, the same evaluator should evaluate subjects at the Baseline and Week 12/ET evaluations.

The evaluator will count all EGW/PAW and identify baseline warts. The location of all warts will be marked on source documents. EGW/PAW will be counted and recorded separately for baseline and all warts. At each study visit, the evaluator will note location of all warts, including new warts that have arisen since the last subject visit.

#### 4.2.1 WART COUNTS

EGW/PAW counts will be captured separately and the location of the warts marked on source documents. The baseline warts and the total wart counts will be counted at Baseline and all post-treatment visits. EGW/PAW that arise during the study will be identified, marked on source documents and reported separately for post-baseline visits.

If an EGW/PAW clears during treatment, as determined by the Investigator, the subject will discontinue study drug application for that specific EGW/PAW, but other EGW/PAW will continue to be treated. For baseline warts that clear during treatment, the Investigator will assess recurrence of treated and cleared EGW/PAW on subsequent study visits.

If all warts (those present at baseline and new warts that develop during the study) clear, as determined by the Investigator, the subject will not continue to apply study drug and will remain in the study for all scheduled post-baseline assessments to assess for wart recurrence.

### 4.3 TOLERABILITY ASSESSMENTS

The Investigator will evaluate the subject's genital/perianal area prior to the first application of investigational product in addition to evaluating at each study visit. The tolerability assessment for visits other than Baseline should be performed at least 30 minutes after study drug application and prior to wart counts. Tolerability evaluations will include erythema, edema, erosions/ulceration and burning/stinging. Burning/stinging will be based on the subject's report

of local symptoms for the previous 24 hours. The highest severity of each parameter will be recorded. Tolerability endpoints will not be reported as an AE unless they reach severe and/or result in subject's discontinuation from the study. Tolerability assessments will be performed according to the following scales:

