### 1.5 SUMMARY OF BENEFITS AND RISKS

External warts (EGW) and perianal warts (PAW) are sexually transmitted diseases caused by infection with papillomaviruses. In the Shope Cottontail rabbit animal model, topical application of NVN1000 Gel inhibited growth of wild type and mutant papillomavirus (Coggan, 2014).

Nitric oxide released from NVN1000 is anticipated to be pharmacologically active in the skin with no systemic exposure to NVN1000 or nitric oxide. In a 5-day cross-over pharmacokinetic study in adults with moderate to severe acne in which NVN1000 Gel at a final concentration of 8% (SB204) was applied to 17% BSA, there was no systemic exposure to NVN1000 and no difference in serum nitrate levels following repeated topical administration.

Dermal toxicology studies have demonstrated minimal evidence of toxicity in a 13-week miniature pig study, low dermal irritation in rabbits, and no dermal sensitization in guinea pigs. Local application site events in a 13-week dermal toxicology study in rats led to premature discontinuation of all dose groups in a time-dependent manner. These local adverse effects seen in the rat study are species specific and monitorable. Tolerability will be assessed during the planned study, and discontinuation criteria for intolerance by subjects is described in Section 6.7.

The independent DSMB will monitor safety and tolerability.

Topical application has been associated with local application-site reactions including erythema, peeling, scaling, or burning/stinging. These local application-site reactions may occur due to the active agent (NVN1000) or the vehicle. Local application-site events including erosions and contact dermatitis were reported in subjects with psoriasis treated with NVN1000 Gel and Vehicle Gel under occlusion and in two subjects in the first cohort dosed in this study with NVN1000 Gel 8% or Vehicle Gel. Within 2 weeks of dosing, these subjects developed severe erythema, burning or erosions leading to treatment discontinuation. At the time of this protocol amendment, it is unknown which treatment these subjects received.

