### 3.1.2 TOLERABILITY ENDPOINTS

The tolerability assessments include the Investigator's assessment of erythema, edema, erosions/ulcers, and the subject's report of burning/stinging based on the preceding 24 hours on a 4-point (0-3) scale (Section 4.3).

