### 6.2 REPORTING ADVERSE EVENTS

For the purpose of AE reporting the trial period is defined as the period after the subject signs the informed consent to the end of subject's last visit.

The Investigator will assess subjects at each scheduled study visit for the occurrence of AEs. In order to avoid bias in eliciting AEs, subjects should be asked the following non-leading question: "How have you felt since your last visit?" All AEs (serious and non-serious) reported by the subject must be recorded on the subject's study record and entered into the study database.

In addition, PPD must be notified within 24 hours of the Investigator's knowledge of the event by telephone or email of any immediately reportable events according to the procedure outlined below. Special attention should be paid to recording hospitalizations and concomitant therapies and medications.

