### 7.6 TOLERABILITY ANALYSIS

Tolerability assessments (erythema, edema, erosions/ulcerations, burning/stinging) will be summarized using frequency distributions at Baseline, Weeks 2, 4, 8, and 12/ET, as well as the worst post-baseline assessment. The number and proportion of subjects with a severe assessment or a two step severity increase from baseline will be summarized by treatment group at Weeks 2, 4, 8 and 12/ET for each assessment and for any assessment. In addition, shift tables will be presented.

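### Mild or moderate local reactions that settle between visits get no tolerability grade and, under Protocol 4.3, no AE record, although Protocol 6.1 and 6.2 would record them

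*Protocol*

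**What the plan says.** **Grading.** The Schedule of Events (Protocol Table 4) has tolerability evaluations at Baseline and Weeks 2, 4, 8 and 12/ET, with Week 2 at Day 14 ± 3. Protocol 3.1.2 combines the investigator's assessment of the three signs with "the subject's report of burning/stinging based on the preceding 24 hours on a 4-point (0-3) scale". Protocol 4.3 adds "The highest severity of each parameter will be recorded" but names no period for it.

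**AE exemption.** Protocol 4.3 continues: "Tolerability endpoints will not be reported as an AE unless they reach severe and/or result in subject's discontinuation from the study".

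**General AE rules.** Protocol 6.1 defines an AE without a severity threshold. Protocol 6.2 has the site ask "How have you felt since your last visit" and then requires: "All AEs (serious and non-serious) reported by the subject must be recorded on the subject's study record".

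**Analysis.** Protocol 7.6 has the scores "summarized using frequency distributions at Baseline, Weeks 2, 4, 8, and 12/ET, as well as the worst post-baseline assessment". SAP 8.3 explains that the worst post-baseline value is chosen across visits, separately for each parameter.

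**Other traces.** Sites identify reasons for missed applications from Week 2 (Protocol 4.1.3). SAP 7.2.1 tabulates and lists doses missed for tolerability. Protocol 5 records concomitant therapy and says that a new one may call for an AE entry. Premature discontinuation triggers the full Week 12/ET evaluation (Protocol 4.1.7).

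**DSMB.** It reviews each cohort after the first 12 subjects have completed two weeks (Protocol 2.1), or about two weeks after the 12th is randomized (Protocol 3.2).

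**The concern.** Tolerability is a named objective and guides the dose reviews. The protocol's own experience is that limiting local reactions come early. Of two Cohort 1 subjects, Protocol 1.5 says: "Within 2 weeks of dosing, these subjects developed severe erythema, burning or erosions leading to treatment discontinuation". The first two weeks are therefore the period of most interest, and it normally ends with a single scheduled score per subject.

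A moderate reaction that starts in the first week and has healed by the visit can be graded 0. Protocol 4.3 tells the site not to enter it as an AE, while 6.2 read alone tells the site to enter it. Two consequences follow:

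- Non-severe reactions can be under-counted in the tolerability tables, so the error is towards good tolerability.
- Sites that give weight to different sections would record different events, so TEAE rates for local reactions would depend partly on site practice.

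**Working it through.** The documents give no detection, incidence or duration figure for tolerability, so there is no stated number to reproduce. The check has two parts.

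**1. Where can a local reaction be recorded?**

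- *Severe, or leading to discontinuation:* an AE under 4.3. Discontinuation also triggers an ET tolerability assessment.
- *Mild or moderate, present at a visit:* graded at that visit.
- *Mild or moderate, resolved between visits, with missed doses:* the diary-based table and listing of SAP 7.2.1. This shows that doses were missed for tolerability, but no severity grade.
- *Mild or moderate, resolved between visits, with a new therapy:* the concomitant therapy record, and an AE where the site judges it applicable.
- *Mild or moderate, resolved between visits, with none of these:* no record if 4.3 is followed; an AE if 6.1 and 6.2 are followed and the subject reports it.

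The worst post-baseline score does not recover the last three groups, because it only picks the maximum of the visit scores.

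**2. How much could one visit miss? (Illustration; onset, duration and incidence are assumptions.)**

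Inputs from the documents: visit on Day 14 (window Days 11–17), 24-hour recall for burning/stinging, 12 subjects at 3:1, so 12 × 3/4 = 9 active.

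A reaction that starts on day s and lasts d whole days is visible on day v if s ≤ v ≤ s + d − 1. The recall adds one day for burning/stinging. For the signs I take the visit-day reading.

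- Onset uniform over Days 1–14, v = 14: d/14 for signs, (d + 1)/14 for burning/stinging.
- Onset uniform over Days 1–7, v = 14: max(0, d − 7)/7 and max(0, d − 6)/7.

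| Duration (days) | Onset Days 1–14: signs / burning | Onset Days 1–7: signs / burning |
|---|---|---|
| 2 | 14% / 21% | 0% / 0% |
| 3 | 21% / 29% | 0% / 0% |
| 5 | 36% / 43% | 0% / 0% |
| 7 | 50% / 57% | 0% / 14% |
| 10 | 71% / 79% | 43% / 57% |

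With the visit on Day 17 and onset in Days 1–14, a 3-day reaction is visible 0% / 7% of the time and a 7-day reaction 29% / 36%.

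For the DSMB set of 9 active subjects, assume at most one reaction each and true incidence p, with visibility c = 3/14 (3-day sign) or 7/14 (7-day sign). Expected true count = 9p; expected visible count = 9pc; chance that none is visible = (1 − pc)^9; chance that none occurred = (1 − p)^9.

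| p | True count | Visible, 3-day / 7-day | None visible, 3-day / 7-day | None occurred |
|---|---|---|---|---|
| 20% | 1.8 | 0.39 / 0.90 | 67% / 39% | 13% |
| 40% | 3.6 | 0.77 / 1.80 | 45% / 13% | 1% |
| 60% | 5.4 | 1.16 / 2.70 | 29% / 4% | <0.1% |

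With p = 40% and 3-day reactions, (1 − 0.4 × 3/14)^9 = 0.446, against 0.6^9 = 0.010.

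**The case against.** The case for leaving the plan alone has several good points.

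- **A reader might infer that early reactions are recorded nowhere.** The documents do not support that. Severe or discontinuing reactions are AEs, doses missed for tolerability are tabulated and listed, and new therapy is recorded. A subject who skips doses because of a reaction is therefore flagged. What is lost for that subject is the grade.
- **A reader might take the two Cohort 1 cases as proof of loss.** They show capture. They met both exceptions in 4.3, and Protocol 3.2 says that the Cohort 2 regimen was changed because of them. They support only the point that reactions come early.
- **The visit-day reading of the three signs is inferred.** The sentence on highest severity has no stated period and could be read as covering the time since the last visit. Burning/stinging is not open to that reading, because its 24-hour window is explicit.
- **4.3 can be read as a specific exception to the general rule in 6.2.** That is a fair reading, and then there is no contradiction. But it is the reading under which the reactions drop out. Under the other reading they are AEs. The text does not say which prevails.
- **The DSMB may see more than one score per subject, and more than the scores.** Earlier enrollees may have reached Week 4 by the time of review, and the DSMB outputs are defined in a charter outside these documents (SAP 10). Whether missed-dose data reach the board is unknown. The Schedule of Events first collects the diary at Week 4, although sites review it at Week 2.
- **Keeping low-grade scored reactions out of the AE tables is a legitimate choice.** It avoids counting the same reaction twice. That reason applies only to reactions that were scored.

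What remains is a narrower gap: non-severe reactions in the four scored categories that resolve between visits without discontinuation.

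**Conclusion.** The point holds in this limited form. Followed as written, Protocol 4.3 leaves a between-visit mild or moderate reaction without a grade and without an AE, while 6.1 and 6.2 would record it as an AE. The error is towards under-counting, and it falls on a named objective and possibly on the data used for dose review.

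Its size cannot be stated from the documents. The 21–29% (3-day) and 50–57% (7-day) figures rest on uniform onset over Days 1–14, a Day 14 visit and a visit-day reading of the signs. Other assumptions in the tables give anything from 0% to 79%. A reader might also divide 4 scored days by 84 treatment days (4.8%) and call that the detection rate. It is not one, because detection depends on how long reactions last. Nor do the documents show that the bias is greatest at a poorly tolerated dose.

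This is an inexpensive improvement in what is recorded and does not undermine the design.

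**What to change.** 1. In Protocol 4.3, limit the AE exemption to reactions present and scored at that visit. A local reaction since the last visit that the visit score does not reflect is recorded as an AE, whatever its severity. Add a cross-reference in 6.2 so that the two sections agree.
2. In Protocol 4.3, state the period that the highest-severity grade covers for each of the four parameters.
3. Optionally, add a worst-since-last-visit CRF item (0–3), subject-reported, at least for burning/stinging. Summarise it in SAP 8.3 and give it to the DSMB beside the visit-day score. For the investigator-assessed signs a recalled grade is a weaker measure and should be labelled as such.

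The cost is protocol wording and, with item 3, up to four CRF fields. No new visit or assessor is needed, and a reaction already scored at the visit is not counted again as an AE. The downside is some recall-based data and more low-grade AE records.

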# **Erythema**

Score Description

0-None No evidence of erythema present

1-Mild Slight pink coloration 2-Moderate Definite redness

3-Severe Marked erythema, bright red to dusky dark red in color

### Edema

ScoreDescription0-NoneNo edema

1-Mild Mild edema; barely perceptible

2-Moderate Moderate swelling localized to the wart and immediately adjacent skin
3-Severe Extensive edema that involves non-treatment sites adjacent to treatment area

### **Erosions/Ulceration**

Score Description
0-None No erosions

1-Mild Slight erosions on some treated areas 2-Moderate Erosions over half of the treated areas

3-Severe Extensive full-thickness erosions over most treatment areas; or at least one

area of ulceration

# **Burning/Stinging**

Score Description

0-None No burning/stinging

1-Mild Slight warm, burning/stinging sensation; not very bothersome

2-Moderate Definite warm, burning/stinging sensation that is somewhat bothersome 3-Severe Hot, tingling/sensation that has caused definite discomfort and may have

disturbed sleep

### 4.4 SAFETY ASSESSMENTS

### 4.4.1 ADVERSE EVENTS

AEs will be collected starting after the subject has signed the informed consent and completed any study assessment until the end of the final study visit. The date of onset, date ended, severity, relationship to study drug, therapy required, and action taken regarding study drug and study participation will be reported for each AE.

See Section 6 for additional information regarding the evaluation of adverse events.

### 4.4.2 PHYSICAL EXAM

A brief physical exam will be performed at Screening, Baseline (Day 0) and Week 12/ET. If clinically significant changes in the physical examination from Baseline are noted at the Week 12/ET visit, these will be recorded as adverse events.

### 4.4.3 VITAL SIGNS

Blood pressure and pulse rate will be collected at Screening, Baseline, and at Weeks 2, 4, 8, and 12. Any clinically significant changes in vital signs from Baseline will be recorded as adverse events whether or not drug related.

# 4.4.4 LABORATORY ASSESSMENTS

Chemistry, hematology, and PT/PTT will be collected at Screening, Baseline, and Week 12/ET. Clinically significant changes in lab results post screening will be recorded as adverse events. Subjects with hemoglobin < 10 g/dL at Screening will not be eligible to participate.

### 4.4.5 METHEMOGLOBIN

Methemoglobin will be measured at Screening, Baseline, Week 2 and Week 12/ET using a Masimo Rainbow® SET® Rad-57TM pulse co-oximeter that analyzes methemoglobin levels. The percent methemoglobin will be displayed on the pulse co-oximeter and recorded in the subject's study record and in the study database.

Subjects with confirmed methemoglobin values of > 3.0% at Screening or Baseline will not be eligible to participate in the study. Subjects with confirmed values > 5.0% during the study will be discontinued. A confirmed methemoglobin is defined as at least two readings within 0.5% of each other taken within a 30 minutes period.

Clinically significant changes in methemoglobin will be recorded as adverse events. The adverse event term should reflect the underlying diagnosis or symptoms and not the pulse co-oximeter result itself.

Clinical symptoms and signs of methemoglobinemia in relation to the level of methemoglobin are listed in Table 5.

Table 5: Clinical Symptoms and Signs of Methemoglobinemia in Relation to the Level of Methemoglobin

Level of Methemoglobin	Clinical Symptoms and Signs
<10%	Frequently asymptomatic, occasionally grayish skin
10%-20%	Skin changes such as cyanosis
20%-30%	Dyspnea, headache, anxiety
30%-50%	Dizziness, palpitations, confusion, tachypnea
50%-70%	Seizures, cardiac arrhythmias, metabolic acidosis, coma
>70%	Death

Source: (Boylston, 2002)

### 4.4.6 PREGNANCY TESTING

All WOCBP must have a UPT at Screening and Baseline and if the result is positive, the subject will not be allowed to participate in the study. Refer to Section 6.4 for further information.

A female is considered to be of childbearing potential UNLESS she is post-menopausal (no menses for 24 consecutive months), surgically sterilized, or without a uterus and/or both ovaries.

Pregnancy tests will also be performed at Weeks 4, 8, and 12/ET. If a subject is determined to be pregnant prior to or during Week 12/ET visit, the subject will be discontinued from the study but followed until term. The outcome of the pregnancy, including status of the neonate, will be submitted.

### 4.5 SCREEN FAILURES

A screen failure subject will be a person from whom informed consent is obtained and is documented in writing (i.e., subject signs an informed consent form) but who does not meet the study eligibility requirements. Subjects will be allowed to rescreen once within the 35-day screening period.

#### 4.6 PROTOCOL DEVIATIONS

This study will be conducted as described in this protocol, except for an emergency situation in which the protection, safety, and well-being of the subject requires immediate intervention, based on the judgment of the Investigator (or a responsible, appropriately trained professional designated by the Investigator). In the event of a significant deviation from the protocol due to an emergency, accident, or mistake, the Investigator or designee must contact PPD and the IRB, if applicable, at

the earliest possible time. All deviations as well as actions taken as the result of the significant must be documented.

### 5. PROHIBITED THERAPIES AND MEDICATIONS

Concomitant medications are any prescription or OTC preparations. Use of concomitant medications will be recorded on the concomitant medications study record and study database beginning at the Baseline Visit until the final evaluation (Week 12/ET).

Subjects must not have used anti-wart treatments including topical treatments or procedures as described in Section 3.7.3 for at least 28 days prior to Baseline. These medications/treatments are also prohibited during the trial.

Subjects may not be concurrently on nitroglycerin, drugs associated with methemoglobinemia, drugs to treat EGW/PAW, or drugs/supplements that are nitric oxide releasers (Appendix 1). Subjects who have used an investigational drug or device within 30 days of Baseline should not be enrolled. Subjects must not participate in a different interventional research study during the study period. Any subject who has participated in a previous study with SB204 Gel/NVN1000 Gel is ineligible for enrollment.

Any medication/therapy used by the subject following first application of study product will be considered a concomitant medication/therapy (e.g., aspirin, acetaminophen, birth control pills, vitamins, etc.). Every attempt should be made to keep concomitant medication/therapy dosing constant during the study. Any change to concomitant medications/therapies should be noted on the subject's study record and in the study database. When applicable, an AE should be completed for any subject starting a concomitant medication/therapy after randomization into the study.

### 6. EVALUATION OF ADVERSE EVENTS

### **6.1 DEFINITIONS**

An adverse event (AE) is any untoward medical occurrence (e.g., sign, symptom, disease, syndrome, intercurrent illness, clinically significant abnormal laboratory finding, injury or accident) whether or not considered drug related. Any AE that emerges or worsens following administration of the informed consent and until the end of study participation will be collected. A pre-existing condition is one that is present prior to the start of the study and is to be reported as part of the subject's medical history. It should be reported as an AE only if the frequency, intensity, or the character of the condition worsens during the study.

An adverse event or suspected adverse reaction is considered "unexpected" if it is not listed in the investigator brochure or is not listed at the specificity or severity that has been observed.

A serious adverse event (SAE) includes any event, if in the view of either the investigator or PPD Medical Monitor results in any of the following outcomes:

- Death
- Life-threatening event (i.e., the subject was, in the opinion of the Investigator, at immediate risk of death from the event as it occurred. It does not apply to an AE that hypothetically might have caused death if it were more severe.)
- Persistent or significant disability/incapacity (i.e., the AE results in a substantial disruption of the subject's ability to carry out normal life functions)
- Requires in-patient hospitalization or prolongs hospitalization (i.e., the AE required at least a 24-hour in-patient hospitalization or prolonged a hospitalization beyond the expected length of stay; hospitalizations for elective medical/surgical procedures, scheduled treatments, or routine check-ups are not SAEs by this criterion)
- Congenital anomaly/birth defect (i.e., an adverse outcome in a child or fetus of a subject exposed to the molecule or investigational product before conception or during pregnancy)
- Does not meet any of the above serious criteria but may jeopardize the subject or may require medical or surgical intervention to prevent one of the outcomes listed above (i.e., is a significant or important medical event)

